10.4.1. Adverse Event Definitions and Classifications

Adverse Event

An AE is any untoward medical occurrence in a clinical study participant administered a pharmaceutical (investigational or non-investigational) product. An AE does not necessarily have a causal relationship with the vaccine. An AE can therefore be any unfavorable and unintended sign (including an abnormal finding), symptom, or disease temporally associated with the use of a medicinal (investigational or non-investigational) product, whether or not related to that medicinal (investigational or non-investigational) product. (Definition per ICH).

This includes any occurrence that is new in onset or aggravated in severity or frequency from the baseline condition, or abnormal results of diagnostic procedures, including laboratory test abnormalities.

Any respiratory tract infection that is not due to SARS-CoV-2 infection will be reported as an AE if it occurs between the time of any vaccination through the following 28 days. Any respiratory tract infection recorded as an AE in the eCRF will be excluded from any AE analysis if the molecular test is subsequently found to be positive for SARS-CoV-2. Respiratory tract infections arising from SARS-CoV-2 infection will not be reported as (S)AEs in the Clinical Study Report but will be tabulated separately. In general, (S)AEs caused by molecularly confirmed SARS-CoV-2 infection will be removed at the analysis level from the (S)AE listings and tables and presented separately.

Note: For time period of sponsor's AE collection, see All Adverse Events under Section [8.3.1](#).

Serious Adverse Event

An SAE based on ICH and EU Guidelines on Pharmacovigilance for Medicinal Products for Human Use is any untoward medical occurrence that at any dose:

- Results in death
- Is life-threatening
(The participant was at risk of death at the time of the event. It does not refer to an event that hypothetically might have caused death if it were more severe)
- Requires inpatient hospitalization or prolongation of existing hospitalization
- Results in persistent or significant disability/incapacity
- Is a congenital anomaly/birth defect
- Is a suspected transmission of any infectious agent via a medicinal product
- Is Medically Important*

*Medical and scientific judgement should be exercised in deciding whether expedited reporting is also appropriate in other situations, such as important medical events that may not be immediately life-threatening or result in death or hospitalization but may jeopardize the participant or may require intervention to prevent one of the other outcomes listed in the definition above. These should usually be considered serious.

If a serious and unexpected AE occurs for which there is evidence suggesting a causal relationship between the study vaccine and the event (eg, death from anaphylaxis), the event must be reported as a serious and unexpected suspected adverse reaction even if it is a component of the study endpoint (eg, all-cause mortality).

If a participant receives a positive SARS-CoV-2 result from a private/off-study test during the study, and the positive result occurs within 28 days after vaccination, the event will be reported as an AE. If it occurs after 28 days, the event will be recorded as an SAE only if the event qualifies as serious. The participant can continue in the study if they choose to; however, this must be in accordance with local country and site level recommendations for COVID-19.

Unlisted (Unexpected) Adverse Event/Reference Safety Information

An AE is considered unlisted if the nature or severity is not consistent with the applicable product reference safety information. For Ad26.COV2.S, the expectedness of an AE will be determined by whether or not it is listed in the IB.

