To assess the humoral immune response in peripheral blood of adult participants induced by Ad26.COV2.S administered IM as a 1-dose (5×10^{10} vp) schedule during the 2 nd and/or 3 rd trimester of pregnancy, at all blood collection timepoints.	
 • Serological response to vaccination as measured by ELISA (S-ELISA; EU/mL) and/or equivalent assay, at all blood collection timepoints.
To assess the humoral immune response in peripheral blood of adult participants to Ad26.COV2.S administered IM as a 1-dose (5×10^{10} vp) schedule during the 2 nd and/or 3 rd trimester of pregnancy, 28 days after vaccination.	
 • Serological response to vaccination as measured by VNA titers, 28 days after vaccination.
To evaluate the humoral immune response in adult participants who are vaccine naïve at study entry and receive a booster dose during the study, pre-boost and at selected time points post booster vaccination.	
 • Serological response to vaccination measured by binding (S-ELISA and/or equivalent assay) and/or neutralizing (VNA) antibody titers.
Neonates and Infants	
To assess antibody levels against SARS-CoV-2 in neonates and infants, born to adult participants who have received Ad26.COV2.S during the 2 nd and/or 3 rd trimester of pregnancy, at birth (ie, in cord blood) and at approximately 2 months and 6 months of age.	
 • Serological response to vaccination as measured by ELISA (S-ELISA, EU/mL) and/or equivalent assay, at birth (ie, in cord blood) and at approximately 2 months and 6 months of age.
To assess antibody levels against SARS-CoV-2 in neonates/infants, born to adult participants who have received Ad26.COV2.S during the 2 nd and/or 3 rd trimester of pregnancy, at birth (ie, in cord blood).	
 • Serological response to vaccination as measured by VNA titers at birth (ie, in cord blood).
To assess safety in neonates and infants born to adult participants who have received Ad26.COV2.S, during the 2 nd and/or 3 rd trimester of pregnancy.	
 • SAEs (including Multisystem Inflammatory Syndrome in Children [MIS-C]) and AESIs in neonates and infants from birth approximately 12 months of age. • MAAEs in neonates and infants from birth until 6 months of age. • AEs in neonates/infants leading to study discontinuation from birth until discontinuation.

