AEs leading to discontinuation will be reported throughout the study.

All AEs will be followed until resolution or until clinically stable.

Adverse Events of Special Interest

From the time of local approval of protocol Amendment 3 onwards, post-vaccination TTS is considered to be an AESI. Suspected AESIs (thrombotic events and thrombocytopenia [defined as platelet count below 150,000/ μ L post-vaccination, see Brighton Collaboration Interim Case Definition, 2021]) will be recorded from the moment of vaccination until the end of the study/early withdrawal. An AESI Adjudication Committee with appropriate expertise will be established to evaluate each suspected AESI and determine whether it is a case of TTS (see Section 8.3.6).

Serious Adverse Events

All SAEs, as well as PQC, occurring during the study must be reported to the appropriate sponsor contact person by study site personnel within 24 hours of their knowledge of the event.

Serious adverse events, including those spontaneously reported to the investigator within 30 days after the last dose of study vaccine, must be reported using an SAE form. The sponsor will evaluate any safety information that is spontaneously reported by an investigator beyond the time frame specified in the protocol.

SAEs in adult participants will be assessed and reported throughout the study, from the date of vaccination until end of study or at least 12 months postpartum. SAEs in the neonates/infants will be followed up until end of study (up to approximately 12 months of age).

Information regarding SAEs will be transmitted to the sponsor using the Serious Adverse Event Form and Safety Report Form of the eCRF, which must be completed and reviewed by a physician from the study site and transmitted to the sponsor within 24 hours. The initial and follow-up reports of an SAE should be transmitted electronically or by facsimile (fax). Telephone reporting should be the exception and the reporter should be asked to complete the appropriate form(s) first.

Signs and symptoms of Multisystem Inflammatory Syndrome in Children (MIS-C) will be monitored and reported as SAE from birth until study end in neonates/infants with (suspected) COVID-19 as confirmed by a positive RT-PCR result for SARS-CoV-2, and in neonates/infants of mothers or a close relative with prior (within 4-weeks) or current suspected or confirmed COVID-19. Further details on case definition and reporting of MIS-C in infants can be found in Section 10.7.

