The verbatim terms used in the eCRF by investigators to identify AEs will be coded using the Medical Dictionary for Regulatory Activities (MedDRA). All reported AEs and events-related reactogenicity diary information will be included in the analysis: solicited local at injection site and systemic AEs with onset after vaccination, and unsolicited AEs with onset after vaccination. For each AE, the percentage of participants who experience at least one occurrence of the given event will be summarized by group and overall separately for adult participants (up to at least 12 months postpartum) and their neonates/infants (up to approximately 12 months of age).

Pregnancy-related AEs throughout pregnancy (including gestational diabetes, gestational hypertension, premature rupture of membranes, premature labor, premature uterine contractions, poor or restricted fetal growth, pre-eclampsia, eclampsia, vaginal or intrauterine hemorrhage [non-exhaustive]) will be assessed and analyzed for adult participants by group and overall. The complete list of preferred terms to be included as pregnancy-related AEs will be provided in the SAP.

For SAEs, suspected AESIs and AEs leading to discontinuation throughout the study (from first vaccination until end of the study [at least 12 postpartum]), the percentage of adult participants who experience at least 1 occurrence of the given event will be summarized by group, overall and by phase including post booster (if applicable). For MAAEs (from vaccination until 6 months after

vaccination or until end of study when leading to study discontinuation), the percentage of adult participants who experience at least 1 occurrence of the given event will be summarized by group and overall. SAEs in the neonates/infants from birth until end of study (approximately 12 months of age) will be assessed by group and overall. MAAEs in the neonates/infants (from birth until 6 months of age or from birth until discontinuation [if MAAE is leading to study discontinuation]) will be assessed by group and overall.

Summaries, listings, datasets, or participant narratives may be provided, as appropriate, for those participants who die, who discontinue vaccine due to an AE, or who experience a severe AE, an SAE, or a suspected AESI by group and overall.

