10.7. Appendix 7: Multisystem Inflammatory Syndrome in Children

Multisystem Inflammatory Syndrome in Children (MIS-C)

MIS-C is a serious and potentially fatal condition that can arise in infants and children infected with SARS-CoV-2, and which can result in inflammation of a range of organs. Patients with MIS-C usually present with persistent fever, fatigue and a variety of signs and symptoms including multiorgan (eg, cardiac, gastrointestinal, renal, hematologic, dermatologic, neurologic) involvement, elevated inflammatory markers and, in severe cases, hypotension and shock.

MIS-C may present weeks after an infant is infected with SARS-CoV-2. The infant may have been infected from an asymptomatic contact and, in some cases, the infant and their parent(s)/caregiver(s) may not even know that they have been infected.

Although different presentations have been described, common symptoms include:

- Kawasaki disease-like features: conjunctivitis, red eyes; red or swollen hands and feet; rash; red cracked lips, swollen glands. Coronary artery enlargement and/or aneurysms have been described. Other symptoms include gastrointestinal (abdominal pain or diarrhea) and neurologic (headaches/meningitis) manifestations.
- Toxic shock syndrome-like features with hemodynamic instability.
- Cytokine storm/macrophage activation or hyperinflammatory features.
- Thrombosis, poor heart function, diarrhea and gastrointestinal symptoms, acute kidney injury.
- Shortness of breath suggestive of congestive heart failure.

The Center for Disease Control and Prevention ([CDC 2020h](https://www.cdc.gov/mis-c/hcp/index.html)) issued a Health Advisory on May 14, 2020, that outlines the following case definition for MIS-C (<https://www.cdc.gov/mis-c/hcp/index.html>):

Case definition for MIS-C

- An individual aged <21 years presenting with fever^a, laboratory evidence of inflammation^b, and evidence of clinically severe illness requiring hospitalization, with multisystem (≥ 2) organ involvement (cardiac, renal, respiratory, hematologic, gastrointestinal, dermatologic or neurological); AND
- No alternative plausible diagnoses; AND
- Positive for current or recent SARS-CoV-2 infection by RT-PCR, serology, or antigen test; or exposure to a suspected or confirmed COVID-19 case within the 4 weeks prior to the onset of symptoms.

^a * Fever $>38.0^{\circ}\text{C}$ for ≥ 24 hours, or report of subjective fever lasting ≥ 24 hours

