10.8. Appendix 8: Case Definitions for COVID-19

10.8.1. Adults Case Definition for Moderate to Severe/Critical COVID-19

Case Definition for Moderate COVID-19

- A SARS-CoV-2 positive RT-PCR or molecular test result from any available respiratory tract sample (eg, nasal swab sample, sputum sample, throat swab sample, saliva sample) or other sample.

AND at any time during the course of observation^a:

Any 1 of the following new or worsening signs or symptoms:

- Respiratory rate ≥ 20 breaths/minute
- Abnormal saturation of oxygen (SpO_2) but still $>93\%$ on room air at sea level*
- Clinical or radiologic evidence of pneumonia
- Radiologic evidence of DVT
- Shortness of breath or difficulty breathing

OR

Any 2 of the following new or worsening signs or symptoms:

- Fever ($\geq 38.0^\circ C$ or $\geq 100.4^\circ F$)
- Heart rate ≥ 90 beats/minute
- Shaking chills or rigors
- Sore throat
- Cough
- Malaise as evidenced by 1 or more of the following^{**}:
 - Loss of appetite
 - Generally unwell
 - Fatigue
 - Physical weakness
- Headache
- Muscle pain (myalgia)
- Gastrointestinal symptoms (diarrhea, vomiting, nausea, abdominal pain)
- New or changing olfactory or taste disorders
- Red or bruised looking feet or toes

SpO_2 criteria will be adjusted according to altitude.

^{**} Having 2 or more elements of a symptom (eg, vomiting and diarrhea or fatigue and loss of appetite) is counted only as 1 symptom for the case definition. To meet the case definition, a participant would need to have at least 2 different symptoms.

^a Participants will be asked to undertake the COVID-19 procedures until 14 days after symptom onset (COVID-19 Day 15) or until **resolution of the COVID-19 episode**, whichever comes last (see Section 8.1.2).

Case Definition for Severe/Critical COVID-19

- A SARS-CoV-2 positive RT-PCR or molecular test result from any available respiratory tract sample (eg, nasal swab sample, sputum sample, throat swab sample, saliva sample) or other sample

AND any 1 of the following at any time during the course of observation^a:

- Clinical signs at rest indicative of severe systemic illness (respiratory rate ≥ 30 breaths/minute, heart rate ≥ 125 beats/minute, oxygen saturation [SpO₂] $\leq 93\%$ on room air at sea level*, or partial pressure of oxygen/fraction of inspired oxygen [PaO₂/FiO₂] < 300 mm Hg)

* SpO₂ criteria will be adjusted according to altitude.

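### Section 10.4.1's rule taking SARS-CoV-2-caused (S)AEs out of the (S)AE tables has no exception for MIS-C or suspected AESIs, and contradicts the infant SAE endpoint that names MIS-C

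*Protocol*

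**What the plan says.** Section 10.4.1 of the protocol has two rules on SARS-CoV-2. The first covers respiratory tract infections and is unqualified: "Respiratory tract infections arising from SARS-CoV-2 infection will not be reported as (S)AEs in the Clinical Study Report but will be tabulated separately". The second is broader and is stated to apply in general ("S)AEs caused by molecularly confirmed SARS-CoV-2 infection will be removed at the analysis level from the (S)AE listings and tables and presented separately"). Neither mentions MIS-C or AESIs.

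For infants, Section 3 (and the Synopsis) lists as a secondary endpoint "SAEs (including Multisystem Inflammatory Syndrome in Children [MIS-C]) and AESIs in neonates and infants from birth approximately 12 months of age". Section 8.3.1, under Serious Adverse Events, says that signs and symptoms of MIS-C "will be monitored and reported as SAE from birth until study end in neonates/infants with (suspected) COVID-19 as confirmed by a positive RT-PCR result", and also in infants whose mother or close relative has recent or current COVID-19. Section 9.4.2 has infant SAEs assessed by group and overall with no exclusion, and opens its adverse event analysis with "All reported AEs and events-related reactogenicity diary information will be included in the analysis".

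For adults, Section 3 makes SAEs and AESIs over the whole study a primary endpoint. Section 9.4.2 summarises SAEs and suspected AESIs as two categories side by side. Under Section 8.3.6.1 every thrombosis is a suspected AESI until adjudicated. Under Section 8.3.6 AESIs are reported whatever their cause. Section 10.8.1 also lists "Radiologic evidence of DVT" among the criteria for moderate COVID-19.

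**The concern.** MIS-C is a consequence of the infection that Section 10.4.1 uses as its ground for removal. Section 10.7 states that "MIS-C is a serious and potentially fatal condition that can arise in infants and children infected with SARS-CoV-2". A rule that takes out events caused by confirmed infection, with no exception, therefore takes out an event that an endpoint of this trial names.

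In adults, thrombosis can be a COVID-19 complication and is also the event that the trial's AESI provisions were written to catch. Whether a serious thrombosis stays in the SAE table then depends on a judgement that it was caused by SARS-CoV-2, made in an open-label study without a control group.

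At stake is whether the main SAE tables can be read at face value. Enrolment was stopped early, so single events matter, and a reader who sees an empty MIS-C or thrombosis row would not know that cases had been moved to another table.

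**Working it through.** **MIS-C: the rules side by side**

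1. Section 3: the endpoint is infant SAEs, with MIS-C named as included.
2. Section 8.3.1: MIS-C is recorded as an SAE, expressly in RT-PCR-positive infants.
3. Section 10.7: the case definition accepts four kinds of link to infection, namely RT-PCR, serology, antigen test, or exposure to a case within the 4 weeks before onset.
4. Section 10.8.4: MIS-C is itself a criterion for severe/critical COVID-19 in neonates and infants.
5. Section 10.4.1: (S)AEs caused by molecularly confirmed infection leave the (S)AE listings and tables.

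Applying step 5 to step 3 gives:

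| Evidence linking MIS-C to infection | Molecularly confirmed? | Infant SAE table |
|---|---|---|
| RT-PCR positive | yes | removed |
| Serology only | no | stays |
| Antigen test only | no | stays |
| Exposure only | no | stays |

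The endpoint is split by type of test. Cases with molecular proof of infection leave its SAE table and cases without it remain.

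**Adult thrombosis**

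1. A serious thrombosis is both an SAE and a suspected AESI.
2. Section 10.4.1 names (S)AE listings and tables, so a serious case judged to be caused by confirmed COVID-19 leaves the SAE table.
3. Section 10.4.1 does not mention the suspected-AESI summary of Section 9.4.2. Section 8.3.6 defines AESIs as a kind of AE, so the rule could be read to reach them, but nothing says that it does.
4. Section 10.4.2 has the investigator assess causality to the study vaccine only. The AESI Adjudication Committee decides only whether a case is TTS (Sections 8.3.1 and 8.3.6.1). Attribution to SARS-CoV-2, on which step 2 depends, is assigned to nobody.

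**Size of a one-event shift in the adult SAE table (illustration)**

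The protocol's own related figures are the upper two-sided 95% limits for zero events in Section 9.2 (text and Table 5). The exact formula is 1 − 0.025^(1/N). For N = 40 this is 1 − 0.025^(1/40) = 8.81%. For N = 60, 120 and 240 it gives 5.96%, 3.03% and 1.53%. The stated 8.8%, 6%, 3% and 1.5% are reproduced.

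If the only woman with a given serious event is removed, the row for that event reads 0/N instead of 1/N. The Clopper-Pearson upper limit for 1/N is the 97.5% point of a Beta(2, N − 1) distribution.

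| N | 1/N | Upper limit, event kept | Upper limit, event removed |
|---|---|---|---|
| 22 | 4.5% | 22.8% | 15.4% |
| 40 | 2.5% | 13.2% | 8.8% |
| 60 | 1.7% | 8.9% | 6.0% |
| 120 | 0.8% | 4.6% | 3.0% |
| 240 | 0.4% | 2.3% | 1.5% |

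Here 22 is the size of the Sentinel and Safety Cohorts and the other values are the planning sizes of Table 3. Final enrolment is not given, so only a range can be shown. These figures do not apply to MIS-C, whose denominator is infants in FAS-NVN.

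**The case against.** The strongest reply is that nothing is hidden. The sentence is qualified as general, and the unqualified rule covers respiratory tract infections only. Removed events are still presented, and COVID-19 severity in infants is analysed with definitions that include MIS-C (Sections 9.4.3 and 10.8.4). Section 8.3.1 governs reporting to the sponsor and Section 10.4.1 acts at analysis, so a site can follow both. The Section 9.4.2 sentence on including all reported AEs goes on to list solicited and unsolicited types and was not written with SARS-CoV-2 in mind. No hypothesis is tested and there is no comparator, so no treatment contrast is distorted.

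Much of this stands. A reader might infer that every COVID-related event disappears, or that confirmed MIS-C must be zero in the report. The text supports neither: the rule is general, and the events move to another table. A reader might also infer that thrombosis drops out of the AESI endpoint. That is not shown either: the suspected-AESI summary has no stated exclusion, and listing deep vein thrombosis as a severity criterion does not by itself attribute a given thrombosis to the virus.

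What does not stand is the suggestion that this removes the conflict. The general qualifier gives no criterion for exceptions. Separate presentation does not restore the events to the SAE table of an endpoint that names MIS-C, nor does it cure the split by test type. It is also not a matter left to the SAP, since the protocol itself fixes both the endpoint and the removal rule.

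**Conclusion.** The point holds in a limited form. The removal rule in Section 10.4.1 contradicts the infant endpoint of SAEs including MIS-C and fits poorly with Section 9.4.2. Applied as written, it gives an infant SAE table that omits RT-PCR-confirmed MIS-C and keeps MIS-C supported by other evidence. For adults, it takes a serious thrombosis attributed to confirmed COVID-19 out of the table for a primary endpoint, while leaving its effect on the suspected-AESI summary, and the person making the attribution, undefined.

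The documents do not show that any reported percentage is in fact understated. That would need at least one such event, and none is reported in the protocol. For MIS-C no size can be computed, because neither the number of infants nor the number of cases is given. The adult table above is hypothetical: it assumes one affected woman and shows a single event row. The overall SAE percentage would fall only if she had no other SAE.

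**What to change.** Amend Section 10.4.1 along these lines: all SAEs, all MIS-C cases and all suspected AESIs are included in the main SAE and AESI tables and listings whatever the participant's SARS-CoV-2 status; events attributed to molecularly confirmed SARS-CoV-2 are flagged; these events are also shown in the separate COVID-19 tabulation, and a supplementary SAE table excludes them.

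Two consequential edits are needed. The sentences in Section 10.4.1 on respiratory tract infections should be limited to non-serious events, so that they do not contradict the new text. Section 10.4.1 or 10.4.2 should state who attributes an event to SARS-CoV-2, since the flag depends on it.

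The cost is protocol wording, matching SAP wording and one extra set of tables. No new data are collected and the sponsor's separate presentation is kept. SAE counts in the main tables may be slightly higher.
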